9.2.3 Efficacy Analysis

9.2.3.1 Primary Efficacy Endpoint

The primary efficacy endpoint is the absolute change from Baseline to Week 18 in LFC, or absolute change from Baseline to the ET visit for subjects who terminate the study prematurely. Absolute change from Baseline in LFC will be assessed by analysis of covariance that includes the effects of treatment group, Baseline LFC, and Baseline ALT. Comparison of each active treatment group to placebo will be tested at the 5% level of significance without adjustment for multiple tests. Secondarily, comparison of the 2 active treatment groups with each other will be tested at the 5% level.

9.2.3.2 Secondary Efficacy Endpoints:

The secondary efficacy endpoints of this study include the following:

- 1. Absolute and relative (percent) change in fasting glucose and HbA1c from Baseline to Week 18, or to the ET visit for dropouts.
- 2. $A \ge 30\%$ reduction in LFC from Baseline to Week 18, or to the ET visit for dropouts.
- 3. Percent change in LFC from Baseline to Week 18, or to the ET visit for dropouts.
- 4. Normalization of LFC to <5% at Week 18, or to the ET visit for dropouts.
- 5. A ≥5-percentage point reduction in LFC from Baseline to Week 18, or to the ET visit for dropouts.
- 6. Absolute and percent change in HOMA-IR from Baseline to Week 18, or to the ET visit for dropouts.
- 7. Absolute and percent change in LDL-c, serum triglycerides, and HDL-c from Baseline to Week 18, or to the ET visit for dropouts.
- 8. Absolute and percent change in AST and ALT from Baseline to Week 18, or to the ET visit for dropouts.

- 9. Normalization of ALT (according to clinical laboratory reference ranges) to Week 18, or to the ET visit for dropouts, among subjects with elevated ALT at Baseline.
- 10. Absolute and percent change in Pro-C3 from Baseline to Week 18, or to the ET visit for dropouts, among subjects with elevated Pro-C3 at Baseline.
- 11. Absolute and percent change in the ELF score and each component of ELF (TIMP-1, PIIINP, and HA) from Baseline to Week 18, or to the ET visit for dropouts.
- 12. Absolute and percent change in total bile acids, C4, and FGF19 from Baseline to Week 18, or to the ET visit for dropouts.

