Total bile acid is calculated as the sum of all bile acid measurements and metabolites at a visit for a given subject.

Total Primary Bile Acid

Total primary bile acid is calculated as the sum of cholic acid, chenodeoxycholic acid, glycocholic acid, glycochenodeoxycholic acid, taurocholic acid, and taurochenodeoxycholic acid at a visit for a given subject.

Total Secondary Bile Acid

Total secondary bile acid is calculated as the sum of deoxycholic acid, lithocholic acid, glycodeoxycholic acid, glycolithocholic acid, taurodeoxycholic acid, and tauroolithocholic acid at a visit for a given subject.

Total Ursodeoxycholic Acid

Total ursodeoxycholic acid is calculated as the sum of ursodeoxycholic acid, glyoursodeoxycholic acid, and tauroolithocholic acid at a visit for a given subject.

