5.2.4. Secondary Efficacy Endpoints

- Change from Baseline and percent change from Baseline in fasting glucose from Baseline to Week 18
- Change from Baseline and percent change from Baseline in HbA1c from Baseline to Week 18.
- Proportion of subjects who achieve $\geq 30\%$ relative reduction in LFC as measured by MRI-PDFP from Baseline to Week 18.
- Percent change from Baseline in LFC as measured by MRI-PDFP from Baseline to Week 18.
- Proportion of subjects who normalize LFC to $< 5\%$ as measured by MRI-PDFP at Week 18.
- Proportion of subjects who achieve $\geq 5\%$ absolute reduction in LFC as measured by MRI-PDFP from Baseline to Week 18.
- Change from Baseline and percent change from Baseline in homeostasis model assessment-estimated insulin resistance (HOMA-IR) from Baseline to Week 18.
- Change from Baseline and percent change from Baseline in low-density lipoprotein cholesterol (LDL-c) from Baseline to Week 18.

- Change from Baseline and percent change from Baseline in serum triglycerides from Baseline to Week 18.
- Change from Baseline and percent change from Baseline in high-density lipoprotein cholesterol (HDL-c) from Baseline to Week 18.
- Changes from Baseline and percent change from Baseline in AST from Baseline to Week 18.
- Changes from Baseline and percent change from Baseline in ALT from Baseline to Week 18.
- Changes from Baseline and percent change from Baseline in GGT from Baseline to Week 18.
- Proportion of subjects with elevated ALT at Baseline who normalize ALT at Week 18.
- Proportion of subjects with elevated AST at Baseline who normalize AST at Week 18.
- Change from Baseline and percent change from Baseline in Pro-C3 from Baseline to Week 18 for subjects with elevated Pro-C3 at Baseline.
- Change from Baseline and percent change from Baseline in the enhanced liver fibrosis (ELF) score and each component of ELF (tissue inhibitor of metalloproteinases 1 [TIMP-1], N-terminal pro-peptide of type III collagen [PIIINP], and hyaluronic acid [HA]) from Baseline to Week 18.
- Change from Baseline and percent change from Baseline in total bile acid from Baseline to Week 18.
- Change from Baseline and percent change from Baseline in total primary bile acids (and metabolites) from Baseline to Week 18.
- Change from Baseline and percent change from Baseline in total secondary bile acids (and metabolites) from Baseline to Week 18.

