- Change from Baseline and percent change from Baseline in total ursodeoxycholic acid (and metabolites) from Baseline to Week 18.
- Change from Baseline and percent change from Baseline in 7 α -hydroxy-4-cholesten-3-one (C4) from Baseline to Week 18.
- Change from Baseline and percent change from Baseline in fibroblast growth factor 19 (FGF19) from Baseline to Week 18.

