5.2.5. Secondary Efficacy Analysis

Change and percent change from Baseline in LFC will be summarized by treatment group and study visit. Differences in percent change from Baseline in LFC will be assessed by analysis of covariance that includes the effects of treatment group, Baseline LFC, and Baseline ALT, comparing each active treatment group to placebo, as well as a comparison of the combined active treatment groups vs. placebo. A figure summarizing LS means of percent change from Baseline at Week 18 by treatment group will also be generated.

Changes from Baseline to Week 18 in the laboratory assessments listed as secondary efficacy endpoints (fasting glucose, HbA1c, HOMA-IR, LDL-c, serum triglycerides, HDL-c, AST, ALT,

Pro-C3, ELF, total bile acids, C4, FGF19) will be assessed by analysis of covariance that includes the effects of treatment group and Baseline value, comparing each active treatment group to placebo. For these analyses, missing Week 18 values will be imputed using the methods described in section 3.3.4. For HbA1c, this model will also be run without imputed values. For all bile acid analyses other than total bile acid, all analyses will be performed without imputation. Figures summarizing change from Baseline over time by treatment group will also be generated for these laboratory assessments. The number and percentage of subjects who achieve $\geq 30\%$ relative reduction in LFC as measured by MRI-PDFF from Baseline to Week 18 will be summarized by treatment group and study visit. The proportion of subjects who achieve $\geq 30\%$ relative reduction in LFC as measured by MRI-PDFF from Baseline to Week 18 will be analyzed by logistic regression that includes the effects of treatment group, Baseline LFC, and Baseline ALT. A figure summarizing the proportion of subjects achieving $\geq 30\%$ relative reduction in LFC as measured by MRI-PDFF from Baseline to Week 18 by treatment group will also be generated.

The number and percentage of subjects who normalize LFC to $< 5\%$ as measured by MRI-PDFF at Week 18 will be summarized by treatment group and study visit. The proportion of subjects who normalize LFC to $< 5\%$ as measured by MRI-PDFF at Week 18 will be analyzed by logistic regression that includes the effects of treatment group, Baseline LFC, and Baseline ALT. A figure summarizing the proportion of subjects who normalize LFC to $< 5\%$ at Week 18 by treatment group will also be generated.

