10. PROPOSED TABLES, LISTINGS, AND FIGURES

Summary Tables

Accountability and Baseline Characteristics

- 14.1.1.1 Subject Disposition – All Randomized Subjects
- 14.1.1.2 Protocol Deviations – All Randomized Subjects
- 14.1.2 Demographics and Baseline Characteristics – Safety Set
- 14.1.3 Extent of Exposure and Treatment Compliance – Safety Set
- 14.1.4 Concomitant Medications by ATC Classification and Preferred Term- Safety Set

Efficacy

- 14.2.1.1 Liver Fat Content by Time Point – Efficacy Set
- 14.2.1.2 Liver Fat Content by Time Point – Modified Efficacy Set
- 14.2.1.3 Liver Fat Content by Time Point – Per Protocol Set
- 14.2.2.1 Changes in Fasting Glucose from Baseline to Week 18 – Modified Efficacy Set
- 14.2.2.2 Changes in HbA1c from Baseline to Week 18 – Modified Efficacy Set
- 14.2.2.3 Changes in HOMA-IR from Baseline to Week 18 – Modified Efficacy Set
- 14.2.2.4 Changes in LDL-c from Baseline to Week 18 – Modified Efficacy Set
- 14.2.2.5 Changes in Serum Triglycerides from Baseline to Week 18 – Modified Efficacy Set
- 14.2.2.6 Changes in HDL-c from Baseline to Week 18 – Modified Efficacy Set
- 14.2.2.7 Changes in AST from Baseline to Week 18 – Modified Efficacy Set
- 14.2.2.8 Changes in ALT from Baseline to Week 18 – Modified Efficacy Set
- 14.2.2.9 Changes in Pro-C3 from Baseline to Week 18 – Modified Efficacy Set
- 14.2.2.10 Changes in ELF Score and Components from Baseline to Week 18 – Modified Efficacy Set
- 14.2.2.11.1 Changes in Total Bile Acids from Baseline to Week 18 – Modified Efficacy Set
- 14.2.2.11.2 Changes in Total Primary Bile Acids from Baseline to Week 18 – Modified Efficacy Set
- 14.2.2.11.3 Changes in Total Secondary Bile Acids from Baseline to Week 18 - Modified Efficacy Set
- 14.2.2.11.4 Changes in Total Ursodeoxycholic Acid from Baseline to Week 18 – Modified Efficacy Set
- 14.2.2.12 Changes in C4 from Baseline to Week 18 – Modified Efficacy Set
- 14.2.2.13 Changes in FGF19 from Baseline to Week 18 – Modified Efficacy Set
- 14.2.2.14 Changes in GGT from Baseline to Week 18 – Modified Efficacy Set

Safety

- 14.3.1.1 Overall Summary of Treatment-Emergent Adverse Events– Safety Set
- 14.3.1.2 Treatment-Emergent Adverse Events by System Organ Class, Preferred Term, and Greatest Severity – Safety Set
- 14.3.1.3 Treatment-Emergent Adverse Events Related to Study Drug by System Organ

- Class and Preferred Term – Safety Set

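### The SAP's total ursodeoxycholic acid formula adds the taurine conjugate of lithocholic acid, already counted in total secondary bile acid, and omits the taurine conjugate of ursodeoxycholic acid

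*SAP*

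**What the plan says.** SAP 3.3.7 defines three bile acid sub-totals one after another, each a sum over species at a visit for one subject.

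- Total primary bile acid sums "cholic acid, chenodeoxycholic acid, glycocholic acid, glycochenodeoxycholic acid, taurocholic acid, and taurochenodeoxycholic acid".
- Total secondary bile acid sums free deoxycholic and lithocholic acid and then "glycodeoxycholic acid, glycolithocholic acid, taurodeoxycholic acid, and tauroolithocholic acid".
- For the third: "Total ursodeoxycholic acid is calculated as the sum of ursodeoxycholic acid, glyoursodeoxycholic acid, and tauroolithocholic acid at a visit for a given subject".

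Total bile acid is defined separately, as the sum of everything measured.

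SAP 5.2.4 makes the third sub-total a secondary efficacy endpoint, as change and as "percent change from Baseline in total ursodeoxycholic acid (and metabolites) from Baseline to Week 18". It does the same for the second: "percent change from Baseline in total secondary bile acids (and metabolites) from Baseline to Week 18". SAP 10 gives the ursodeoxycholic endpoint its own output, Table 14.2.2.11.4, "Changes in Total Ursodeoxycholic Acid from Baseline to Week 18". SAP 5.2.5 adds: "For all bile acid analyses other than total bile acid, all analyses will be performed without imputation".

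The endpoint is an SAP addition. The bile acid entry in Protocol 9.2.3.2 is "Absolute and percent change in total bile acids, C4, and FGF19 from Baseline to Week 18", and Protocol Table 2 names only those three items under the bile acid panel.

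**The concern.** A sub-total named for ursodeoxycholic acid should contain that acid and its own conjugates. As written, one of its three terms is a conjugate of a different acid, and that species also sits in the secondary sub-total. A change in the lithocholic conjugate would be reported as a change in ursodeoxycholic acid, and the same change would appear again in the total secondary bile acid table (14.2.2.11.3). Any change in the taurine conjugate of ursodeoxycholic acid would appear in no sub-total.

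This matters more here than a slip in an incidental laboratory variable would. The study drug is a 1:1 salt of berberine and ursodeoxycholic acid (Protocol 1.0), and bile acid homeostasis is a stated secondary objective. This sub-total follows the drug's own component. The independent programming planned in SAP 5 would not necessarily catch the error, because two programmers working from the same written definition would agree on the same sum.

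**Working it through.** The plan states no figure to reproduce here. The check compares the three lists and then derives the error.

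**Step 1. Tabulate the terms in SAP 3.3.7** (irregular spellings normalised).

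| Parent acid | Sub-total | Free | Glycine conjugate | Taurine conjugate |
|---|---|---|---|---|
| Cholic | Primary | yes | yes | yes |
| Chenodeoxycholic | Primary | yes | yes | yes |
| Deoxycholic | Secondary | yes | yes | yes |
| Lithocholic | Secondary | yes | yes | yes |
| Ursodeoxycholic | Ursodeoxycholic | yes | yes | **no: taurolithocholic listed instead** |

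**Step 2. Count.**

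- Terms listed: 6 + 6 + 3 = 15.
- Overlap of primary with secondary, and of primary with ursodeoxycholic: none.
- Overlap of secondary with ursodeoxycholic: one species, taurolithocholic acid, spelled identically in both definitions.
- Distinct species: 15 − 1 = 14.
- Expected if each parent has three forms: 5 × 3 = 15 distinct. The missing one is tauroursodeoxycholic acid, which neither document names anywhere.
- With that one term substituted: 15 listed, 15 distinct, no overlap.

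**Step 3. Look for a reading that saves the definition.** The endpoint's reference to metabolites does not do so. If lithocholic forms were meant as metabolites of ursodeoxycholic acid, free and glycine-conjugated lithocholic acid would belong in the sum too, and both are absent. The primary and secondary endpoints carry the same parenthesis, and their formulas contain only each parent's own conjugates. No other section redefines the sum.

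**Step 4. Derive the error.** Let *I* be the intended total, *W* the total as written, *L* taurolithocholic acid and *T* tauroursodeoxycholic acid. Subscripts 0 and 18 denote Baseline and Week 18.

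- Level: *W* = *I* + (*L* − *T*).
- Change from Baseline: (*W*₁₈ − *W*₀) − (*I*₁₈ − *I*₀) = (*L*₁₈ − *L*₀) − (*T*₁₈ − *T*₀).
- Percent change: put *c* = (*L* − *T*)/*I* at each visit. Then *W*₁₈/*W*₀ = (*I*₁₈/*I*₀) × (1 + *c*₁₈)/(1 + *c*₀). This equals *I*₁₈/*I*₀ only if *c*₁₈ = *c*₀, that is, if the difference between the two species is the same fraction of the intended total at both visits. Nothing in the documents supports assuming that.

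If the laboratory does not report *T*, the total that could actually be computed is the two-species sum. The error against that sum is *L* at each visit and *L*₁₈ − *L*₀ in the change. The overlap with the secondary sub-total remains in either case.

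**The case against.** Four points can fairly be made against this.

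- **The term may be a text-conversion artefact.** Technical terms in the SAP text are irregular elsewhere: MRI-PDFF also appears as MRI-PDFP and MRI-PDF, and two of the three names in the disputed sentence are misspelled. This cannot be excluded without the source document. However, those slips are one or two characters, whereas lithocholic for ursodeoxycholic is a different word, and the string matches the one in the preceding definition exactly.
- **The documents do not show that tauroursodeoxycholic acid is assayed.** This is correct. If it is not, the omission could not have been avoided, but including the lithocholic conjugate and counting it twice would still be wrong.
- **The endpoint carries little weight.** It is absent from the protocol and from the analytes that SAP 5.2.5 names for analysis of covariance. It has no figure, and it feeds neither the interim rules nor the sample size nor any analysis set. All of this stands and limits the importance of the point. The endpoint is nevertheless listed as a secondary efficacy endpoint with its own table, and a descriptive table with the wrong content under its title is still wrong.
- **Size and direction are unknown.** This also stands, and no claim is made about either.

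**Conclusion.** The point holds. As SAP 3.3.7 reads, one of the three terms in total ursodeoxycholic acid belongs to another acid. That term is counted in two sub-totals, and the taurine conjugate of ursodeoxycholic acid is counted in none. An analyst following the rule would produce a variable that is not what its title says.

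The effect is confined to this one SAP-added secondary endpoint and its table. Total secondary bile acid is correctly defined, although its lithocholic taurine conjugate is repeated in the ursodeoxycholic table. Total bile acid sums all measurements, so it would include tauroursodeoxycholic acid if that is assayed.

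The conclusion assumes that the term reads the same in the source SAP and that the parent-plus-own-conjugates pattern, followed for the other four acids, was intended here too.

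**What to change.** 1. Check the disputed term against the source SAP.
2. Confirm from the central laboratory's analyte list whether the bile acid panel reports tauroursodeoxycholic acid.
3. If it does, define total ursodeoxycholic acid as ursodeoxycholic + glycoursodeoxycholic + tauroursodeoxycholic acid. If it does not, define it as the two reported species and say so in a footnote to Table 14.2.2.11.4.
4. In both cases, keep taurolithocholic acid only in total secondary bile acid.
5. Align the derivation programs and the table with the corrected definition before database lock.

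The cost is one term in one definition, one check of the analyte list, one program line and possibly one footnote. No new data are needed and the design does not change.

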3.4. TIMING OF ANALYSES

An interim analysis will be conducted once source document verification is completed for a minimum of 51 subjects who complete the assessment of the primary efficacy endpoint to assess sample size assumptions and futility through conditional power. The study will not be stopped for

efficacy. The method of Cui and colleagues (Cui et al., 1999) will be used to compute the alpha spend associated with the interim analysis to assess futility and to recompute sample size by evaluating the pooled standard deviation for the LFC change from Baseline.

Conditional power calculations will be performed for the difference between each of the two active treatment groups versus placebo for the primary endpoint. The following rules will be applied for the primary efficacy endpoint:

1. If both conditional powers at the time of the interim analysis are $<10\%$, then the study will be terminated for futility.
2. If either conditional power is $>10\%$ but both are $<36\%$, then the sample size will not be increased and the study will continue based on the original sample size.
3. If either conditional power is $>36\%$ but both are $<80\%$, then the sample size will be adjusted to retain the original power of 90% or a 50% increase in the sample size, whichever is smaller.
4. If either conditional power is $>80\%$, then the study will continue as is.

The sponsor will be advised of either futility, no change, or of a specific sample size increase, but not about the degree of efficacy per treatment group. The analysis will be conducted by an independent statistician who is not otherwise involved in the operational aspects of this study.

The final analysis will be completed after the last subject completes or discontinues the study and the resulting clinical database has been cleaned, quality checked, and locked.

Additionally, safety oversight will be conducted throughout the study under the direction of a DSMB. The timing and frequency for the DSMB will be detailed in a separate DSMB charter.

4. ANALYSIS SETS

The sets for analysis will include the Efficacy set, the Modified Efficacy set, the Per Protocol Set, and the Safety set.

4.1. EFFICACY SET

The Efficacy set will consist of all randomized subjects who complete at least 80 days of study drug dosing and have a Week 18 (or ET) visit MRI-PDFP assessment. Subjects in this set will be analyzed according to the treatment to which they were randomized. This set will be utilized for analyses of efficacy.

4.2. MODIFIED EFFICACY SET

The Modified Efficacy set will consist of all randomized subjects who receive at least one dose of study drug and who have at least one post-dose MRI-PDFP assessment. Subjects in this set will be analyzed according to the treatment to which they were randomized. This set will be utilized for analyses of secondary endpoints, as well as select analyses of the primary endpoint.

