9.2.2 Analysis Datasets

The efficacy dataset will consist of all randomized subjects who meet the following conditions:

- For analysis of the primary efficacy endpoint, randomized subjects who complete at least 80 days of study drug dosing and have a Week 18 (or ET) visit MRI-PDFF assessment.
- For analysis of the secondary efficacy endpoints, randomized subjects who receive at least one dose of study drug and have at least one post-dose assessment.

The safety dataset will include all randomized subjects who receive at least one dose of study drug.

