Percent change from Baseline in LFC will be analyzed by the same model described for the primary efficacy endpoint. Normalization of LFC, a \geq 30% reduction in LFC, and a 5-percentage point reduction in LFC will each be analyzed by a logistic regression that includes the effects of treatment group, Baseline LFC, and Baseline ALT.

All additional secondary efficacy endpoints are continuous and each will be assessed by analysis of covariance that includes treatment group and the Baseline value of the analysis variable. All secondary analyses (except LFC) will have missing Week 18 values imputed using a multiple imputation procedure for all subjects with an available measurement prior to Week 18.

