3.3.4. Missing Data and Outliers

Every effort will be made to obtain required data at each scheduled evaluation from all subjects who have been treated. For subjects who do not complete the 18-week evaluation, endpoints that will only be measured at Week 18 or the Early Termination (ET) visit (i.e., LFC, HOMA-IR, Pro-C3, ELF) will have the value at the ET visit carried forward for the missing Week 18 visit.

For all non-LFC secondary endpoints measured at at least one post-baseline timepoint other than Week 18/ET, missing Week 18 values will be imputed using a multiple imputation procedure for all subjects with an available measurement prior to Week 18. Multiple imputation relies on the assumption that the data are missing at random. This method of imputation produces unbiased estimators of the mean and standard error, and, as such, is preferred over single imputation methods. For this method, the procedure requires production of multiple datasets containing plausible values for each missing value. These plausible values are generated using available auxiliary information (site, treatment, baseline assessment value, baseline LFC, and baseline ALT).

Using a set of values rather than a single value better accounts for the uncertainty about the value being imputed. For this imputation, the Markov chain method will be used. SAS PROC MI will be used to generate 10 possible imputed datasets.

For each variable that has imputations performed, the following steps will be followed:

1. Missing values will be imputed using PROC MI. This will result in 10 datasets per variable.
2. Efficacy endpoints will be derived from the appropriate set of 10 datasets produced by PROC MI using the imputed values.
3. Each efficacy endpoint will be analysed 10 times (once per source dataset) using the appropriate statistical model for that endpoint.
4. For each endpoint, the results from the analysis from each of the 10 datasets will be combined using PROC MIANALYZE to produce an inferential result for the parameter of interest.

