The number and percentage of subjects who achieve $\geq 5\%$ absolute reduction in LFC as measured by MRI-PDFF from Baseline to Week 18 will be summarized by treatment group and study visit. The proportion of subjects who achieve $\geq 5\%$ absolute reduction in LFC as measured by MRI-PDFF from Baseline to Week 18 will be analyzed by logistic regression that includes the effects of treatment group, Baseline LFC, and Baseline ALT. A figure summarizing the proportion of subjects who achieve $\geq 5\%$ absolute reduction in LFC from Baseline to Week 18 by treatment group will also be generated.

The number and percentage of subjects with elevated ALT at Baseline who normalize ALT at Week 18 will be summarized by treatment group and study visit. The proportion subjects of with elevated ALT at Baseline who normalize ALT at Week 18 will be analyzed by logistic regression that includes the effects of treatment group, Baseline LFC, and Baseline ALT. A figure summarizing the proportion of subjects who normalize ALT at Week 18 by treatment group will also be generated. For this analysis, missing Week 18 values will be imputed using the multiple imputation method as described in section 3.3.4.

If the data is not amenable to analysis by logistic regression for any of the responder endpoints included in this section, then comparisons between treatment groups may be performed using Cochran-Mantel Haenszel (CMH) testing instead.

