7. CHANGES IN THE PLANNED ANALYSES

No deviations in the conduct of the study or the planned analysis are anticipated. Should any deviations from the analyses specified in the authorized statistical analysis plan arise, such deviations will be documented in the final clinical study report.

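### The SAP requires a final MRI for every secondary laboratory analysis, where the protocol requires only one post-dose assessment, so it removes dropouts whom both documents say will be imputed

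*SAP*

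**What the plan says.** **Analysis set.** Protocol 9.2.2 defines the secondary-endpoint population as "randomized subjects who receive at least one dose of study drug and have at least one post-dose assessment". SAP 4.2 replaces the second condition: subjects must be those "who have at least one post-dose MRI-PDFP assessment" (the scan named there is taken to be MRI-PDFF). SAP 4.2 assigns this set to the secondary endpoints, and the table list in SAP section 10 follows it. All of Tables 14.2.2.1 to 14.2.2.14 carry that label, for example "Changes in HbA1c from Baseline to Week 18 – Modified Efficacy Set".

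**Imputation.** Protocol 9.2.3.2 states: "All secondary analyses (except LFC) will have missing Week 18 values imputed using a multiple imputation procedure for all subjects" who have an earlier measurement. SAP 3.3.4 says of non-LFC endpoints with an interim visit that "missing Week 18 values will be imputed using a multiple imputation procedure for all subjects with an available measurement prior to Week 18". SAP 5.2.5 applies this to ALT normalisation as well: "missing Week 18 values will be imputed using the multiple imputation method as described in section 3.3.4". It also makes an exception: "For all bile acid analyses other than total bile acid, all analyses will be performed without imputation".

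**Declared changes.** SAP section 7 lists none. It says "No deviations in the conduct of the study or the planned analysis are anticipated".

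**The concern.** HbA1c, glucose, lipids and liver enzymes do not need a liver scan. Under the SAP, whether a subject counts in those analyses nevertheless depends on a post-randomisation event, having a final scan. The subjects most likely to lack one are those who left early, and they are the subjects that the imputation plan is meant to keep. Their data would still appear in listings, and their chemistry in Safety-set summaries, but they would drop out of the secondary inference.

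There is also a question about subjects who do attend an ET visit. The documents do not agree on whether their observed ET laboratory value stands as the Week 18 value or is replaced by an imputed one. Two programmers could work from different Week 18 values for the same subject.

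**Working it through.** **1. Who differs between the two sets.** Protocol Table 1 and the SAP 1.2 schedule give the visits:
- Chemistry (glucose, ALT, AST): Weeks 2, 6, 10, 14 and 18/ET.
- HbA1c, lipids and the bile acid panel: Weeks 10 and 18/ET.
- HOMA-IR, Pro-C3 and ELF: Week 18/ET only after Baseline.
- MRI-PDFF: Week 18/ET only after Baseline.

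A subject who stops after an interim visit and has no ET scan meets the Protocol 9.2.2 condition and fails the SAP 4.2 condition. SAP 4.1 is no way round this, because the Efficacy set needs an MRI and 80 days of dosing.

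**2. What is left to impute.** Everyone in the SAP 4.2 set has a post-dose scan, hence normally a Week 18 or ET visit. Protocol 5.1.5 makes ET procedures the same as Week 18 procedures, blood samples included.
- If ET counts as Week 18, little remains to impute beyond isolated missing samples. The extra HbA1c run without imputed values (SAP 5.2.5) would nearly repeat the main run.
- If ET does not count as Week 18, imputation replaces observed ET values.

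**3. The plan's own figure.** Inputs from Protocol 9.2.6: difference 5, SD 6.3, two-sided 5%, power 90%.
- Normal approximation: n = 2 × (1.960 + 1.282)² × (6.3/5)² = 33.4, so 34 per group.
- By the t-test, power is 89.7% at 34 and 90.5% at 35, so the stated 35 reproduces.
- 35/0.90 = 38.9, so 39 per group; 3 × 39 = 117.

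**4. Size of the mismatch.** Planned dropouts are 0.10 × 117 = 11.7 (equivalently 3 × (39 − 35) = 12). Let s be the share of dropouts with an ET scan. The documents do not give s, so it is varied. The number outside the SAP set is 11.7 × (1 − s).

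| s | Outside the set | Set size |
|---|---|---|
| 0 | 11.7 | 105.3 |
| 0.5 | 5.9 | 111.2 |
| 0.8 | 2.3 | 114.7 |
| 1 | 0 | 117 |

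The number who lose a usable interim value for a given endpoint is smaller, because some dropouts leave before that endpoint's first post-dose visit. Anyone who attends Week 18 or ET, gives blood and has no scan comes on top; no count of these can be derived.

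**5. Treatment of an observed ET value.**

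| Place | LFC | HOMA-IR, Pro-C3, ELF | Glucose, HbA1c, lipids, enzymes, total bile acids |
|---|---|---|---|
| Protocol 9.2.3.2, endpoint list | ET value | ET value | ET value |
| SAP 3.3.6 | ET value | ET value | ET value |
| Protocol 9.2.4, with the 9.2.3.2 analysis paragraph | ET value | Imputed | Imputed |
| SAP 3.3.4 | ET value | ET value | Imputed |

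The first two rows agree in effect, so there are three outcomes. Protocol 9.2.3.2 falls on both sides.

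**6. Imputation inputs.** SAP 3.3.4 makes an earlier measurement the entry condition for imputation. Its list of inputs names site, treatment, the endpoint's baseline value, baseline LFC and baseline ALT. It does not say whether the earlier post-dose values enter the model.

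**The case against.** **The SAP may refine the protocol.** Protocol 9.2.1 leaves detail to the SAP, so a narrower set is not an error in itself. That is fair, but this set also conflicts with the SAP's own imputation plan in section 3.3.4, and no passage provided declares or explains the change.

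**The effect may be small or nil.** ET visits include the MRI, and Protocol 8.3 asks sites to try hard to complete them. This stands, and it is why the range starts at zero.

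**An imputed dropout may add little.** If earlier post-dose values do not enter the imputation model, a dropout contributes little beyond baseline information, and removing that subject should change the ANCOVA little. This also stands. The set mismatch has real weight only if those values are used. SAP 3.3.4 calls its list auxiliary information, so it may simply be additional to the endpoint's own series.

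**The ET passages can be partly reconciled.** A reader might infer four rival rules; the table shows three outcomes. A reader might also see a firm conflict over HOMA-IR, Pro-C3 and ELF. However, Protocol 9.2.4 describes a class of endpoints measured only at Week 18 or ET, and SAP 3.3.4 can be read as completing the members of that class. SAP 3.3.6 is written for summary displays. A coherent reading exists (place ET at Week 18, then impute what is still missing), but no passage states that order. Independent programming checks (SAP section 5) make an unnoticed divergence less likely; they do not choose the rule.

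**SAP section 7 is not a certificate.** A reader might take it as a statement that the SAP matches the protocol. It looks ahead to departures from the SAP. It shows only that the change of set is not listed there.

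**Conclusion.** The set mismatch holds and should be fixed. At the planned 10% dropout it puts 0 to about 12 of 117 subjects outside the secondary laboratory analyses, assuming that every non-dropout is scanned and leaving the ET-scan share open.

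Finer counts per endpoint are tempting but not supported:
- They need an assumed timing of dropout.
- It is unclear whether C4 and FGF19 fall under the no-imputation exception in SAP 5.2.5.
- The later bile acid panels apply only to subjects with a Baseline panel.
- ALT normalisation concerns only subjects with elevated Baseline ALT.

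Nor do the documents support a claim that the secondary results would be biased in a particular direction or by a particular amount. The primary analysis, its sample size and its power are untouched. The affected endpoints are secondary and tested without multiplicity adjustment in a proof-of-concept study.

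The ET question is real but lesser. The clearest gap concerns endpoints with interim visits (glucose, HbA1c, lipids, enzymes, total bile acids), where an observed ET value may be used or replaced. The imputation inputs are missing detail, not a contradiction.

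**What to change.** 1. For non-LFC secondary endpoints, use the Protocol 9.2.2 condition and relabel the 14.2.2.x tables to match. Keep the MRI condition for LFC endpoints only.
2. State in SAP 3.3.4 that an observed ET value is used as Week 18 and that only values still missing are imputed, or state another single rule. Align Protocol 9.2.3.2, Protocol 9.2.4, SAP 3.3.4 and SAP 3.3.6 to it, or record the departure from the protocol in SAP section 7.
3. In the same edit, say whether the endpoint's own earlier post-dose values enter the imputation model; naming them as inputs would settle it.

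Items 1 and 3 cost SAP wording and programming; the data are already collected under the schedule. Item 2 also needs the protocol text aligned or the section 7 entry. All three should be settled before unblinding.
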